9.2.2. Approach to the Subject with an Efficacy Outcome Event

If a subject has a suspected efficacy outcome event during the study, the treating physician should exercise clinical judgment and follow established guidelines to apply the standard of care. At the treating physician's discretion, the routine measures described below may be considered.

- Temporarily interrupt or permanently discontinue study drug treatment as clinically indicated. Unblinding of study drug should not be necessary, as anticoagulation regimens do not require adjustment regardless of treatment group assigned when study drug is administered in the doses used in this study.
- Perform necessary diagnostic procedures and consider the usual treatment measures for VTE and/or cardiac ischemic events if physical examination and diagnostic testing suggest benefit could be obtained.

After clinical evaluation of the suspected efficacy outcome event is completed restarting study drug may be considered if none of the conditions requiring permanent discontinuation are present (Section [10.2.3](#), Permanent Discontinuation of Study Treatment), and after consultation with the medical monitor. In the event that a decision is made to restart study drug (Section [10.2.1](#), Temporary Interruption of Study Treatment), guidelines for restarting study drug

(Section 10.2.2, Approach to Subjects with Temporary Interruption of Study Treatment) may be followed if applicable based on the clinical judgment of the investigator.

9.3. Pharmacokinetics

9.3.1. Evaluations

Pharmacokinetic samples will be collected at selected countries and sites that can provide the logistical requirements necessary for the PK sampling. Fasting is not required to validate the population PK model. Four sparse blood samples will be collected at 2 visits for about 600 subjects (300 subjects in rivaroxaban subjects [200 subjects in the 10 mg daily and 100 in the 7.5 mg daily group] and 300 in the placebo group) (Table 3 and Table 4). These data will be used to describe drug exposure. Blood samples (2.0 mL each) for determination of rivaroxaban plasma concentrations will be collected at the time points indicated in the TIME AND EVENTS SCHEDULE. The exact date and time of the administration of the current dose (plus the 2 preceding doses) and the precise actual time of blood sample collection must be accurately documented in the eCRF or laboratory requisition form, as appropriate. The PK sub-study will only be conducted at specific sites (ie, those that have the capability to draw, process, and store the PK samples), where all subjects screened will be given the choice to participate. For the PK sample population, drug should always be taken in the morning. At the Day 7 visit, the study drug must be administered under supervision following the collection of the trough sample. At the Day 21 visit, subjects will take the study medication at home in the morning and visit the clinic for PK sampling. At the Day 21 visit, the date and time of the dose administration must be recorded and there needs to be a minimum of 3 hours between sample collections. Subjects may be confined to the study site during PK sampling, if considered appropriate. Samples will be used to evaluate the PKs of rivaroxaban (Attachment 3).

Table 3 Pharmacokinetic Suggested Sampling Schedule

PK Blood sampling (selected sites and subjects)	Day 7		Day 21	
	Pre-dose	Hours Post-dose	Hours Post-dose	
		1-4 Hours	3-7 Hours	7-12 Hours
	X	X	X	X

Table 4: Summary of PK Suggested Observations for Rivaroxaban Arm

Active doses (mg/day)	Total number of subjects with measured samples on Rivaroxaban	Number of Measurements Plasma Concentrations
7.5	100	400
10	200	800
Total	300	1,200

9.3.2. Analytical Procedures

Pharmacokinetics

Plasma samples will be analyzed to determine concentrations of rivaroxaban using a validated, specific and sensitive liquid chromatography coupled to tandem mass spectrometry (LC-MS/MS) method.

9.3.3. Pharmacokinetic Parameters

Based on the individual plasma concentration-time data, using the actual dose taken and the actual sampling times, PK parameters and exposure information of rivaroxaban will be derived using population PK modelling. Baseline covariates (eg, lean body mass, age, serum creatinine) will be included in the model.

9.4. Medical Resource Utilization and Health Economics

Medical resource utilization and health economics data collection will include re-hospitalization (including ER visits, intensive care unit and cardiac care unit stays), length of stay and subject discharge destination (after re-hospitalization).

9.5. Safety Evaluations and Outcomes

9.5.1. Bleeding Events

The study will include the following evaluations of safety and tolerability according to the time points provided in the [TIME AND EVENTS SCHEDULE](#): ISTH major bleeding, non-major clinically relevant bleeding, other bleeding, adverse events, and clinical laboratory tests.

The study will use the ISTH Bleeding Event Classification Scale to assess bleeding events as major, non-major clinically relevant bleeding, or other bleeding. Similar to efficacy outcomes, the same independent CEC will adjudicate and classify bleeding events according to definitions in the CEC charter. The CEC will also classify bleeding events using the Bleeding Academic Research Consortium scale as a supportive approach.²⁷

The principal safety outcome for this study is major bleeding using validated ISTH bleeding criteria. Other safety outcomes are non-major clinically relevant bleeding and other bleeding.

An ISTH major bleeding event is defined as overt bleeding that is associated with:

- A fall in hemoglobin of 2 g/dL or more, or
- A transfusion of 2 or more units of packed red blood cells or whole blood, or
- A critical site: intracranial, intraspinal, intraocular, pericardial, intra-articular, intramuscular with compartment syndrome, retroperitoneal, or
- A fatal outcome

Non-major clinically relevant bleeding is defined as overt bleeding not meeting the criteria for major bleeding but associated with medical intervention, unscheduled contact (visit or telephone call) with a physician, (temporary) cessation of study treatment, or associated with discomfort for the subject such as pain or impairment of activities of daily life.

Examples of non-major clinically relevant bleeding are:

- Epistaxis if it lasts for more than 5 minutes, if it is repetitive (ie, 2 or more episodes of true bleeding, ie, not spots on a handkerchief, within 24 hours), or leads to an intervention (packing, electrocautery, etc.)
- Gingival bleeding if it occurs spontaneously (ie, unrelated to tooth brushing or eating), or if it lasts for more than 5 minutes
- Hematuria if it is macroscopic, and either spontaneous or lasts for more than 24 hours after instrumentation (eg, catheter placement or surgery) of the urogenital tract
- Macroscopic gastrointestinal hemorrhage: at least 1 episode of melena or hematemesis, if clinically apparent
- Rectal blood loss, if more than a few spots
- Hemoptysis, if more than a few speckles in the sputum, or
- Intramuscular hematoma
- Subcutaneous hematoma if the size is larger than 25 cm² or larger than 100 cm² if provoked
- Multiple source bleeding

Other bleeding is defined as any other overt bleeding episodes that do not meet the ISTH criteria for major or non-major clinically relevant bleeding.

Details of all bleeding events will be captured in the eCRF.

All suspected bleeding events will be submitted for adjudication.

9.5.2. Approach to the Subject with a Bleeding Event

If a subject has a serious bleeding event during study drug treatment, the following routine measures should be considered:

- Delay the next study drug administration, or discontinue treatment if indicated. Rivaroxaban has a plasma half-life of approximately 5 to 9 hours, and in some subjects up to 13 hours. Therefore, temporary cessation of study drug may allow control of bleeding. Unblinding of study drug should not be necessary. As there is not a specific reversal agent for rivaroxaban, management of the subject should not be impacted by knowledge of study drug treatment.
- Consider the usual treatment measures for bleeding events, including fluid replacement and hemodynamic support, blood transfusion, and fresh frozen plasma, if physical examination and laboratory testing suggest benefit could be obtained.
- Consider that other causes besides antithrombotic medication can be contributory to the seriousness of the bleeding event (i.e., rule out disseminated intravascular coagulation,

thrombocytopenia, and other coagulopathies; kidney and liver dysfunction; concomitant medications, etc.), and treat accordingly.

If bleeding cannot be controlled by these measures, consider administration of 1 of the following procoagulants (according to the dosages advised in their respective package inserts).⁴³

- Activated prothrombin complex concentrate
- Prothrombin complex concentrate
- Recombinant factor VIIa (NovoSeven[®])

Any products administered to control bleeding should be entered in the CRF.

Note: Protamine sulfate and vitamin K are not expected to affect the anticoagulant activity of rivaroxaban. There is currently no scientific rationale for benefit, or experience with systemic hemostatics (eg, desmopressin, aprotinin, and epsilon aminocaproic acid).

After resolution of the bleeding event, restarting study drug may be considered based on the clinical judgment of the investigator.

9.5.3. Other Safety Assessments

Adverse Events

Adverse events will be reported by the subject (or, when appropriate, by a caregiver, surrogate, or the subject's legally acceptable representative) for the duration of the study. Adverse events will be followed by the investigator as specified in Section 12, Adverse Event Reporting.

Clinical Laboratory Tests

Separate laboratory screening tests are not expected to be performed by the investigator as these will likely be part of the subjects' hospital evaluation. No pre-specified laboratory tests will be performed for the duration of the study. However, these subjects are likely to have local laboratory tests performed during their index hospitalization. Any laboratory test along with reference ranges relevant to a serious adverse event or an outcome event should be recorded on the appropriate eCRF page.

The following tests results with reference ranges will be obtained from the hospital laboratory/local laboratory at the time of the index hospitalization:

- hematology
 - hemoglobin
 - platelet count
- serum creatinine (CrCl to be calculated by IWRS using Cockcroft-Gault formula⁶)
- D-dimer
- serum or urine pregnancy testing for women of childbearing potential only

9.6. Benefit-Risk Balance

Benefit-risk balance of rivaroxaban will be explored. Refer to Section 11.8, Benefit-Risk Analysis for details.

9.7. Sample Collection and Handling

The actual dates and times of sample collection must be recorded in the eCRF or laboratory requisition form. If blood samples are collected via an indwelling cannula, an appropriate amount (1 mL) of fluid slightly greater than the dead space volume of the lock will be removed from the cannula and discarded before each blood sample is taken. After blood sample collection, the cannula should be managed per local practice.

Refer to the [TIME AND EVENTS SCHEDULE](#) for the timing and frequency of all sample collections.

10. SUBJECT COMPLETION/WITHDRAWAL

10.1. Completion

The total duration for a subject who completes the study after randomization is expected to be 75 days.

All feasible efforts and measures will be made to collect complete vital status and other outcome data from randomization to the Day 75 ($\pm 5d$) visit for each subject randomized in this study, regardless of compliance with study drug or visits. For subjects who are lost to follow-up or withdraw consent from the study, efforts will be made to obtain their vital status and other outcomes from permitted sources.

It is important to note that withdrawal of consent does not withdraw permission to collect vital status and other outcomes. Withdrawal of permission to collect vital status and other outcomes must be made separately. In cases where subjects indicate they do not want to “continue”, investigators must determine whether this refers to discontinuation of study treatment (the most common expected scenario), unwillingness to attend follow-up visits, unwillingness to have telephone contact, unwillingness to have any contact with study personnel, or unwillingness to allow contact with a third party (eg, family member, doctor). In all cases, every effort must be made to continue to follow the subject, and vital status and other outcomes must be determined for all randomized subjects.

10.2. Discontinuation of Study Treatment

If a subject's study treatment must be discontinued before the end of the double-blind treatment phase, the subject must continue to be followed for efficacy and safety outcomes.

During the study, should the subject develop any condition, which in the investigator's judgment requires long-term anticoagulation thromboprophylaxis, or fibrinolysis, the subject will have study treatment either temporarily interrupted or permanently discontinued and will be managed as deemed appropriate by the treating physician. The subject will be asked to continue in the study to be followed for efficacy and safety outcomes.

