As described in Section 1.1.5, 3 studies have been conducted testing an extended period of thromboprophylaxis. For each of these studies, a post-hospital discharge placebo comparator was used, and none provided evidence of a benefit/risk balance better than placebo. The MARINER study will enroll a population at greater risk of VTE and lower risk of bleeding than previously studied, and will use the placebo comparator as the standard of care, as recommended by the

ACCP. Given the ACCP guidelines, the duration of thromboprophylaxis in these patients is usually determined by the duration of hospitalization, as it is unusual for patients to receive thromboprophylaxis after discharge. In fact, in the MARINER study, patients for whom thromboprophylaxis is prescribed after discharge are specifically excluded.

Based on the above, placebo has been chosen as the appropriate comparator to allow for the evaluation of benefit/risk of rivaroxaban as thromboprophylactic agent in post-hospital discharge high-risk, medically ill patients.

Any patient with a medical condition that will require chronic use of any parenteral or oral anticoagulation (eg, atrial fibrillation) during the study is not eligible for participation. During the study, should the subject develop any condition, which in the investigator's judgment requires long-term anticoagulation, thromboprophylaxis, or fibrinolysis, the subject will have study treatment either temporarily interrupted or permanently discontinued and will be managed as deemed appropriate by the treating physician. The subject will be asked to continue in the study to be followed for efficacy and safety outcomes.

Dose Selection

The selection of a dose of 10 mg daily of rivaroxaban is based primarily on the results of the studies conducted for prophylaxis of VTEs in patients undergoing knee or hip replacement surgery, where 10 mg daily of rivaroxaban resulted in benefit with an acceptable risk profile.

Subjects with CrCl ≥ 50 mL/min will be randomly assigned to receive rivaroxaban 10 mg daily or placebo. In order to reduce the risk of bleeding in subjects with a baseline CrCl ≥ 30 mL/min and < 50 mL/min (estimated to be approximately 20% of study population), a dose adjustment of rivaroxaban from 10 mg daily to 7.5 mg daily will be implemented (Section 3.1)

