4.3. Prohibitions and Restrictions

Potential subjects must be willing and able to adhere to the following prohibitions and restrictions during the course of the study to be eligible for participation. If subjects require or take prohibited medications during the study as outlined below, they must either temporarily interrupt or permanently discontinue the study drug, as appropriate for the duration of the therapy with the prohibited medication:

Note: Numbered criteria in brackets are for data collection purposes and are intentionally non-sequential.

- [2.2] Combined P-gp and strong CYP3A4 inhibitors (such as but not limited to ketoconazole, telithromycin or protease inhibitors) use within 4 days before randomization, or planned use during the study. Itraconazole use is prohibited within 7 days before randomization and during the study.
- [3.2] Combined P-gp and strong CYP3A4 inducers (such as but not limited to rifampin/rifampicin, rifabutin, rifapentine, phenytoin, phenobarbital, carbamazepine, or St. John's Wort) use within 2 weeks before randomization, or planned use during the study.
- [4.1] Anticoagulant (eg, warfarin sodium or other vitamin K antagonists, Factor II or Xa inhibitors) is prohibited as concomitant therapy during the study. Study drug should be discontinued in subjects who develop any condition which requires anticoagulation or thromboprophylaxis (eg, atrial fibrillation, VTE) that will extend beyond the end of the study treatment phase.

- [6.1] Fibrinolytic therapy (see Section 10.2.1 for guidance)
- [7.1] Use of antiplatelet therapy, including:
 - a. ASA >162 mg/day
 - b. Clopidogrel > 75 mg/day or ticlopidine > 250 mg twice daily
 - c. Clopidogrel at any dose in combination with omeprazole or esomeprazole
 - d. Dipyridamole >400 mg/day
 - e. Cilostazol >200 mg/day
 - f. Dual therapy with 2 or more antiplatelet agents (dipyridamole with ASA is permitted)
 - g. Other P2Y12 receptor antagonists (eg, prasugrel, ticagrelor)
 - h. Thrombin-receptor antagonists (eg, vorapaxar)
 - i. Prescribed daily non-steroidal anti-inflammatory drugs (temporary use as needed is allowed).
- [9] Modification of an effective pre-existing therapy should not be made for the explicit purpose of entering a subject into the study.

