10.2.1. Temporary Interruption of Study Treatment

If the subject requires re-hospitalization (re-hospitalization is defined as a combined total of inpatient and/or ER stay ≥ 24 hours) during the study drug treatment for reasons other than the primary efficacy outcome or bleeding, the subject should be maintained on the study drug at the discretion of the investigator. If the treating physician feels that the subject requires any anticoagulation during the re-hospitalization, study drug needs to be temporarily interrupted, and can be resumed upon hospital discharge. Mechanical methods of prophylaxis may be used during hospitalization. If this method is chosen, study drug may be continued.

In addition, the study drug should be temporarily interrupted if the subject:

- Develops any medical condition that may require use of anticoagulant therapy, thromboprophylaxis, fibrinolysis or poses an increased bleeding risk.
- Undergoes percutaneous coronary intervention, coronary artery bypass graft, any other interventional procedure, that may require use of anticoagulant therapy, thromboprophylaxis, or poses an increased bleeding risk. For temporary interruption of study drug for an elective procedure or surgery, it is suggested that investigators follow measures in [Table 4](#) and [Table 5](#) (Section 10.2.2 Approach to Subjects with Temporary Interruption of Study Treatment).
- Experiences a major bleeding event other than intracranial bleeding. For less severe bleeding events, investigator discretion is allowed. If possible, study drug should be resumed when the bleeding event has resolved and the cause has been identified and corrected.
- If a subject develops a new neurologic deficit or significant alteration in mental status suggesting a cerebral vascular accident. Once a diagnosis is definitively made and appropriate treatment is provided, the study drug may be restarted at the discretion of the investigator.
- Develops a platelet count less than 50,000/ μL . If a repeat platelet count is obtained, and the result indicates that the abnormal platelet count was spurious, study drug may be restarted. If the finding was not spurious, study drug may be restarted after 2 consecutive values greater than 75,000/ μL at least 1 week apart have been obtained.
- Has a serious adverse event that is considered by the investigator to be possibly related to, or exacerbated by, study drug administration.

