10.2.3. Permanent Discontinuation of Study Treatment

If a subject must be permanently discontinued from study drug before the end of the double-blind treatment phase, this will not result in automatic withdrawal of the subject from the study, and the subject should continue to be followed for efficacy and safety outcomes (for details see Section 3.1).

A subject should be permanently discontinued from study drug if:

- The investigator believes that for safety reasons (ie, adverse event) it is in the best interest of the subject to stop study drug.
- The subject develops any condition which requires anticoagulation or thromboprophylaxis extending beyond the treatment phase of the study (eg, atrial fibrillation, VTE).
- The subject becomes pregnant.
- The subject has a fall in CrCl to below 20 mL/min or 2 consecutive measurements less than 30 mL/min at least 1 week apart (as calculated by Cockcroft-Gault formula, see Section 9.1.2) during the study.
- The subject requires hemofiltration or dialysis on a permanent basis
- The subject requests to discontinue study drug permanently
- The subject has a hemorrhagic stroke, or intracranial bleeding

If the subject permanently discontinues study drug before Day 45, he/she should be instructed to complete an unscheduled visit and the remaining scheduled visits, including the Day 7 and Day 21 visits (if not yet completed), and Day 45 (+4d) and Day 75 (\pm 5d) visits (Section 9.1.3). The Day 45 visit should be a clinic visit; the Day 75 visit may be a telephone visit.

The eCRF is to be completed to identify the reason for permanent discontinuation of study drug. The investigator will provide a narrative to describe any adverse events that occur up to the Day 75 (\pm 5d) visit. The appropriate adverse event or serious adverse event sections of the eCRF

are to be completed. If study drug is terminated for a serious adverse event, expedited reporting (within 24 hours) is also required as outlined in Section 12.3.2, Serious Adverse Events.

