16. ETHICAL ASPECTS

16.1. Study-Specific Design Considerations

Potential subjects will be fully informed of the risks and requirements of the study and, during the study, subjects will be given any new information that may affect their decision to continue participation. They will be told that their consent to participate in the study is voluntary and may be withdrawn at any time with no reason given and without penalty or loss of benefits to which they would otherwise be entitled. Only subjects who are fully able to understand the risks, benefits, and potential adverse events of the study, and provide their consent voluntarily will be enrolled.

This study was designed to closely mimic current clinical practice of discontinuing anticoagulation at hospital discharge. Over 90% of post-discharge patients do not continue thromboprophylaxis with anticoagulants. Furthermore, thromboprophylactic treatment is limited by the growing trend for shorter hospital stays (see Section 1.1). As VTE events still occur post-hospital discharge, there is a need to evaluate the current standard of care. A placebo comparator group is therefore justified to evaluate this post-discharge treatment paradigm. The bleeding risk will be reduced in this high risk medically ill population through dose adjustment and exclusion of patient subgroups with a comparatively higher bleeding risk, eg, active cancer (see Exclusion Criteria Section 4.2).

Any subject with a medical condition that requires use of any parenteral or oral anticoagulation (eg, atrial fibrillation) during the study is not eligible for participation. During the study, should the subject develop any condition which in the investigator's judgment requires anticoagulation, fibrinolysis, or thromboprophylaxis, the subject will have study treatment discontinued and will be managed as deemed appropriate by the treating physician. The subject will be asked to continue in the study to be followed for efficacy and safety outcomes.

Rivaroxaban has been studied in over 70,000 patients for treating or preventing thrombotic associated diseases. Because the safety profile of rivaroxaban and the risk of bleeding with its use are well known, blood draws were kept to a minimum in this fragile group of subjects. Subjects will undergo all other treatments and diagnostic tests according to the standard of care in their locality, thus making this study minimally intrusive in their regular routine health care.

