2.3. Analysis set and Analysis Phase

Each analysis involves the following 2 aspects: 1) analysis set, specifying the subjects to be included; and 2) analysis phase, specifying the time window within which data will be included.

Key analysis sets and analysis phases are defined below.

Analysis sets

- Intention-to-Treat (ITT) (as termed Full Analysis Set in the International Conference on Harmonisation [ICH] E9 guideline): This analysis set consists of all randomized subjects who have a signed valid informed consent.
- Per-Protocol (PP): This analysis set is a subset of the ITT analysis set.

Subjects with the key protocol deviations will be excluded from the PP analysis set. The categories and terms of the key protocol deviations will include the following:

- Did not meet the following inclusion or met the following exclusion criteria;
 - INT-2, INT-3, INT-4: subject with index hospitalization > 14 days, inclusion criteria 1, 2, 4, 6, exclusion criteria 10, 11, 14, 22, 24, 27
 - INT-6, INT-7: inclusion criteria 1.2, 2.2, 4.3, 6.1, exclusion criteria 10.2, 11.1, 14.1, 22.2, 24.2 without c
- Did not take any assigned study drug or took wrong study drug
- Did not discontinue study drug permanently according to the protocol (The subject becomes pregnant, develops any condition which requires permanent anticoagulation, has a fall in CrCl to below 20 mL/min during the study, or has a hemorrhagic stroke or intracranial bleeding)
- Had been taking prohibited concomitant therapies as specified in the protocol
 - INT-2: 2, 3,
 - INT-3, INT-4: 2, 3, 4, 6, 7, 8
 - INT-6, INT-7: 2.2, 3.2, 4.1, 7.1 without c and i

- Safety: This analysis set is a subset of the ITT analysis set, consisting of subjects who receive at least one dose of study drug.

Analysis phases

- Up-to-Day-45: This analysis phase includes all data from randomization to Day 45 (inclusive).

For time to event analyses, subjects who do not have events to be analyzed on or before Day 45 will be censored on Day 45 or the last outcome-evaluation date whichever occurs first.

- On-Treatment: This analysis phase includes all data from randomization to 2 days after the last dose of the study drug (inclusive).

For time to event analyses, subjects who do not have events to be analyzed during this phase will be censored on the last dose + 2 or the last outcome-evaluation date whichever occurs first.

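### The protocol's sections disagree on whether study drug is interrupted or discontinued when a subject comes to need anticoagulation, and the SAP's key-deviation wording does not match the protocol's rule

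*Protocol*

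**What the plan says.** **Short-term need.** For a re-hospitalized subject who requires anticoagulation, protocol 10.2.1 says that "study drug needs to be temporarily interrupted, and can be resumed upon hospital discharge". Section 6 likewise lets the investigator restart at discharge. The list in 10.2.1 of reasons to interrupt also includes a subject who "Develops any medical condition that may require use of anticoagulant therapy, thromboprophylaxis, fibrinolysis or poses an increased bleeding risk", with no statement of duration, and a temporary need for a prohibited therapy.

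Section 16.1 covers the same ground differently. If a condition arises that "requires anticoagulation, fibrinolysis, or thromboprophylaxis, the subject will have study treatment discontinued". It gives no duration and no option to interrupt.

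**Longer need.** Section 10.2 says that if a condition "requires long-term anticoagulation thromboprophylaxis, or fibrinolysis, the subject will have study treatment either temporarily interrupted or permanently discontinued". The synopsis repeats this, and 3.2 has the same rule: "requires long-term anticoagulation, thromboprophylaxis, or fibrinolysis, the subject will have study treatment either temporarily interrupted or permanently discontinued". Section 10.2.3 lists as a reason for permanent discontinuation: "The subject develops any condition which requires anticoagulation or thromboprophylaxis extending beyond the treatment phase of the study (eg, atrial fibrillation, VTE". Section 4.3, item 4.1, says study drug should be discontinued for a condition requiring anticoagulation or "thromboprophylaxis (eg, atrial fibrillation, VTE) that will extend beyond the end of the study treatment phase".

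**SAP.** Section 2.3 makes failure to stop permanently according to the protocol a key deviation that removes the subject from the per-protocol set. One of the situations it names is a subject who "develops any condition which requires permanent anticoagulation".

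**The concern.** These are operative instructions to sites on whether a subject goes back on blinded drug. Re-hospitalization is foreseeable in this population: the protocol collects it as a resource outcome and writes dosing rules for it. If two sites can follow two sections and treat the same subject differently, delivered exposure depends on which page was read.

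Three planned analyses take that difference in directly:
- The on-treatment phase (last dose plus 2 days) is used for the principal safety outcome, ISTH major bleeding, and for the per-protocol sensitivity analysis of the primary outcome.
- The compliance rate in SAP 4.3 treats interruption days under 10.2.1 differently from days lost after a permanent stop.
- Per-protocol membership depends in part on whether the subject should have been stopped permanently, and the SAP judges this with a trigger that is not the protocol's.

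**Working it through.** The plan gives no figure to reproduce. The check is a side-by-side reading of the current text, followed by one worked example.

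| Place | Trigger | Action on study drug |
|---|---|---|
| Protocol 6; 10.2.1 (re-hospitalization) | anticoagulation given in hospital | interrupt, may resume at discharge |
| Protocol 10.2.1, first listed reason | condition that may need anticoagulation, duration not stated | interrupt |
| Protocol synopsis, 3.2, 10.2 | long-term need | either |
| Protocol 4.3, lead-in | prohibited medication required or taken | either, according to duration of that therapy |
| Protocol 4.3, item 4.1 | need extends past the treatment phase | discontinue |
| Protocol 10.2.3 | need extends past the treatment phase | discontinue permanently |
| Protocol 16.1 | any need | discontinue |
| SAP 2.3 | permanent anticoagulation | failure to stop permanently is a key deviation |

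**Case 1, short inpatient course.** Sections 6 and 10.2.1 interrupt and allow resumption. Section 16.1 discontinues.

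**Case 2, time-limited course running past Day 45 (for example after a VTE).** Section 10.2.3 stops permanently and 4.3 item 4.1 discontinues. The first listed reason in 10.2.1 interrupts. The synopsis, 3.2 and 10.2 allow either if the course counts as long-term. The SAP's phrase does not apply on a plain reading, because the need is not permanent.

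**Case 3, indefinite need (for example new atrial fibrillation).** Section 10.2.3 stops permanently. The synopsis, 3.2 and 10.2 still allow interruption.

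**What the difference does to the analysis.** Illustrative subject, with assumptions: first dose on Day 1, prophylactic heparin on Days 15 to 19, no other missed doses, no outcome event, followed to the end of the study.

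*Interrupted and resumed (10.2.1):*
- Doses taken: 45 − 5 = 40 of 45.
- SAP 4.3 compliance: actual = 45 − 1 + 1 − 5 = 40; intended = 45 − 1 + 1 − 5 = 40; rate = 40/40 = 100%.
- On-treatment window: last dose Day 45, plus 2 = Day 47. All five heparin days fall inside it.
- SAP 4.2: treatment completer.

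*Stopped for good (16.1, if discontinued is read as permanent):*
- Doses taken: 14 of 45.
- SAP 4.3 compliance: actual = 14 − 1 + 1 = 14; intended = 45 − 1 + 1 = 45; rate = 14/45 = 31%.
- On-treatment window: last dose Day 14, plus 2 = Day 16. Two heparin days fall inside it.
- SAP 4.2: treatment non-completer.

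The at-risk period for major bleeding for this one subject differs by 47 − 16 = 31 days.

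**The case against.** The strongest reply is that the working rule is already coherent. The sentence in 10.2 can be read as introducing its two subsections: 10.2.1 for temporary need and 10.2.3 for need beyond the treatment phase. Item 4.1 of 4.3 draws the same line as 10.2.3, and the 4.3 lead-in ties the choice to how long the prohibited therapy lasts. Section 16.1 is a summary in the ethics section, and it says discontinued, not permanently discontinued.

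Much of this stands. Sections 10.2.1 and 10.2.3 can be reconciled with each other, and the worked example depends on reading 16.1 as a permanent stop. It does not remove the conflict. On its own words, 10.2 permits interruption for a long-term need, and a need outlasting a 45-day phase is hard to class as anything else. Section 16.1 omits both the duration qualifier and the interruption option found in the parallel sentences of the synopsis, 3.2 and 10.2.

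The documents do not support four stronger readings that a reader might infer:
- *That subjects could receive rivaroxaban together with another anticoagulant.* Item 4.1 of 4.3 prohibits concomitant anticoagulants, and every passage cited has study drug interrupted or stopped. After a suspected efficacy event, 9.2.2 allows a restart only if no 10.2.3 condition is present, and after consulting the medical monitor. A general bleeding-hazard claim is not warranted.
- *That the SAP wording lets wrongly continued subjects stay in the per-protocol set.* SAP 2.3 has a separate key deviation for prohibited therapies, which lists item 4.1 for INT-6 and INT-7. It would catch most of them.
- *That there are several competing triggers for a permanent stop within the protocol.* Long-term in 10.2 is not such a trigger, because interruption is allowed, and 16.1 does not say permanent.
- *That the primary analysis is compromised.* ITT Up-to-Day-45 counts subjects as randomized, whatever treatment they received.

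**Conclusion.** The point holds as an inconsistency in operative instructions. It has two parts in the protocol: interrupt and resume against discontinue for a short need, and either action against a permanent stop for a need running past the treatment phase. There is also a smaller mismatch in SAP 2.3.

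It is more than clerical, because it decides whether a subject resumes blinded drug. For an affected subject, the on-treatment window could end on Day 47 or Day 16, and compliance could be 100% or 31%, under the assumptions of the example and with 16.1 read as a permanent stop. The definition of the primary analysis does not change; only the exposure behind it does. Because the choice is made blind, I would not expect it by itself to favour one arm.

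The number of subjects affected cannot be derived. The documents give no re-hospitalization rate, no share of those subjects given anticoagulation, and no indication of how many sites would apply 16.1 over the more specific 10.2.1.

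**What to change.** Reconcile the protocol synopsis, 3.2, 4.3 item 4.1, 10.2, 10.2.1, 10.2.3 and 16.1 so that one instruction covers a need for anticoagulation, thromboprophylaxis or fibrinolysis that ends within the treatment phase, and one covers a need that extends beyond it. State in each place whether discontinued means permanently. Then replace the permanent-anticoagulation phrase in SAP 2.3 with the protocol's trigger words. Which handling is right in each situation is a clinical matter for the sponsor.

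The cost is wording in a protocol amendment and one phrase in the SAP. No new procedures, data or subjects are needed.
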